### **21.3.7 Variables Derived From Data of the Screening Log**

Time from the first Ozurdex implant injection to the most recent follow-up visit prior to 01 September 2018

The variable will be calculated in days as:

Date of the most recent follow-up visit prior to 01 September 2018 – Date of the first Ozurdex injection. As dates are collected in format MM/YYYY, '01' will be considered for the day in the calculation.

### **21.4 IMPUTATION OF MISSING DATA**

Partial date fields with missing day will be imputed as the first of the month. Partial date fields with missing day and month will be imputed as 01JUL.

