## 10.3 Medical and Ophthalmic History

Chronic medical conditions and medical conditions ongoing at time of first Ozurdex implant injection will be collected, along with year of onset. History of glaucoma, cataract and lens status (phakic or pseudophakic) will be collected.

DME history, i.e. date of onset of symptoms and date of DME diagnosis in the study eye, will be collected.

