### 21.3.4 Variables Related to Times and Durations

#### Convention

Time calculated in days will be converted in months using the convention:

$$1 \text{ month} = 365.25 \div 12 \text{ days} = 30.4375 \text{ days}$$

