#### Time to baseline

For a given event E, the time from the event E to baseline will be derived in months as:

$$(\text{Date of the first Ozurdex injection in the study eye} - \text{Date of Event E}) \div (365.25 \div 12). \text{ The result will be rounded to 0.1.}$$

This derivation rule will be applied for the following times calculated in months: time from DME diagnosis to baseline, time from onset of DME symptoms to baseline, time from onset of glaucoma to baseline, time from onset of ocular hypertension to baseline, time from the last retinal laser treatment to baseline, time from the last retinal surgery to baseline, time from the last anti-VEGF/Corticosteroid treatment to baseline.

The time from diabetes diagnosis to baseline will be derived in years as:

$$(\text{Date of the first Ozurdex injection in the study eye} - \text{Date of diabetes diagnosis}) \div 365.25. \text{ The result will be rounded to 0.1.}$$

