### Duration of AESI

The duration will be derived in days as: End date of AESI – Onset date of AESI +1.

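### Year-only history dates are set to 1 July with no ceiling at the first injection, so some events known to precede baseline get negative times to baseline

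*SAP*

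**What the plan says.** SAP 21.4 has two rules for incomplete dates. When only the day is missing: "Partial date fields with missing day will be imputed as the first of the month". When day and month are missing: "Partial date fields with missing day and month will be imputed as 01JUL". There is no exception for events known to precede baseline, and no check of the imputed date against any other date.

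SAP 21.3.4 uses these dates as follows: "For a given event E, the time from the event E to baseline will be derived in months as" the date of first injection minus the date of the event, divided by 365.25/12 and rounded to 0.1. It continues: "This derivation rule will be applied for the following times calculated in months: time from DME diagnosis to baseline". The list goes on to DME symptoms, onset of glaucoma and of ocular hypertension, last retinal laser, last retinal surgery and "time from the last anti-VEGF/Corticosteroid treatment to baseline". Time from diabetes diagnosis has the same form in years. No floor at zero is stated.

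These events are prior history by construction. SAP 13.0 defines prior medication and surgery as taken before the first injection in the study eye, and SAP 21.3.6 names the ophthalmic history form as covering the time before that injection.

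For AESIs, SAP 21.3.4 says "The duration will be derived in days as: End date of AESI" minus onset date plus 1.

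**The concern.** A mid-year imputation is reasonable when nothing more is known than the year. Here more is known: the event came no later than the first injection. If that injection was given between January and June and the event carries the same year, 1 July lies after the injection. The rule then discards the known order and returns a value that cannot be true.

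The variables concerned describe who is being treated: how long since DME was diagnosed, and how long since the last anti-VEGF, corticosteroid or laser treatment. The affected records are those whose event is closest to baseline, so the error falls on recently diagnosed or recently treated eyes. A negative time since last prior treatment in a baseline table would be visibly wrong. If the SAP is silent, whoever programs the table has to choose a correction after seeing the data.

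**Working it through.** **Inputs.** The rule for missing day and month is 1 July (SAP 21.4). Time to baseline is (first injection - event) / (365.25/12) (SAP 21.3.4). Baseline is the day of the first injection (SAP 21.2). First injections fall after 1 January 2015 (inclusion criterion 3) and up to 1 September 2017 (SAP 4.0).

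**The plan's own figure.** "Time calculated in days will be converted in months using the convention" 1 month = 30.4375 days. 365.25 / 12 = 30.4375, so it reproduces exactly.

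**Single records.** Take an event recorded only by year, in the same year as the injection. Its true time to baseline must lie between 0 and the time elapsed since 1 January.

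| First injection | Injection minus 1 July (days) | Rule gives (months) | True value lies in (months) |
|---|---|---|---|
| 2 Jan 2015 | -180 | -5.9 | 0 to 0.0 |
| 15 Feb 2015 | -136 | -4.5 | 0 to 1.5 |
| 15 Mar 2015 | -108 | -3.5 | 0 to 2.4 |
| 15 May 2015 | -47 | -1.5 | 0 to 4.4 |
| 30 Jun 2015 | -1 | 0.0 after rounding | 0 to 5.9 |
| 15 Sep 2015 | +76 | 2.5 | 0 to 8.4 |
| 1 Jan 2016 | -182 | -6.0 | 0 |

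For example, a true event on 10 January 2015 with injection on 15 March 2015 is 64 / 30.4375 = 2.1 months; the rule returns -108 / 30.4375 = -3.5. The extreme, -182 / 30.4375 = -6.0 months, is -0.5 years on the scale used for diabetes diagnosis.

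**Exposed injection dates.** From 2 January 2015 to 1 September 2017 there are 364 + 366 + 244 = 974 dates. Those before 1 July of their year number 180 + 182 + 181 = 543, or 55.7%. On those dates a same-year, year-only event gets on average -3.0 months, if injections are spread evenly over the window.

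**Share of year-only records.** The documents give no distribution of event times, so this part is assumption. Let the injection fall at fraction u of the year, uniform on 0 to 1, and let the event be uniform over the preceding L years. A record goes negative when u < 0.5 and the event is in the same calendar year.

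- L = 1: the same-year probability is u, so the share is the integral of u from 0 to 0.5 = 0.125.
- L = 0.5: the probability is 2u, so the share is 0.25.
- L of 1 or more: 0.125 / L, giving 2.5% at 5 years and 1.25% at 10 years.

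For L = 1 or 0.5, the negative records have mean u = (0.125/3) / 0.125 = 1/3. Their imputed mean is 1/3 - 1/2 = -1/6 year, or -2 months; their true mean is u/2 = +1/6 year, or +2 months. (The -3.0 above weights all exposed injection dates equally; -2 weights them by the chance that the event falls in the same year.) Over all year-only records with L = 1 the mean is unchanged, because the event is then uniform over its own calendar year and mid-year is its mean.

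**Scale in patients.** Suppose, purely for illustration, that 10% of dates are year-only and all 150 patients have the event. Then 150 x 0.10 x 0.25 = 3.75 patients at L = 0.5; 150 x 0.10 x 0.125 = 1.9 at L = 1; and 150 x 0.10 x 0.025 = 0.4 at L = 5. These counts move in proportion to the year-only rate.

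**Missing day only.** The first of the month is never later than the true date, so this rule cannot push a prior event past baseline.

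**AESI duration.** With onset on 20 March and an end date recorded only as March of the same year, the end becomes 1 March and the duration is 1 - 20 + 1 = -18 days. This needs a complete onset date and an end date in the same month lacking only its day. If both days are missing, both become the 1st and the duration is 1 day.

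**The case against.** The strongest reply is that the problem is rare and sits away from anything that matters. Three conditions must meet: a year-only date, an event in the injection year, and an injection before 1 July. For the variables at issue the protocol asks for dates: DME symptoms and diagnosis (10.3), laser (10.4.2) and last intravitreal treatment (10.4.3), and the DME diagnosis date is in the minimum required dataset (8.2.4). This stands.

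A reader might point to Protocol 10.3, where conditions are collected "along with year of onset", as proof that year-only dates are expected for these variables. It does not show that. The phrase concerns chronic and ongoing medical conditions, which SAP 10.3 summarises by SOC and PT and which have no time-to-baseline variable. What the documents do show is that SAP 21.4 provides for year-only dates in a retrospective chart review, so they are possible.

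A reader might also take 12.5% or 25% as a share of patients, or conclude that quartiles and SDs are materially wrong. Neither follows. The percentages apply only to year-only records, under the assumed spread of events. No quartile or SD has been computed, and with a few affected records the lower quartile would hardly move.

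It can further be said that safeguards exist. Protocol 12 builds on-line logic checks into data entry, and SAP 21.5 provides a documented outlier review before lock. But the first acts on entered dates, not on dates imputed at analysis, and the second makes no adjustment and sets no rule. Site queries are ruled out because patients cannot be re-identified. These measures might expose a negative value; they do not say what to do with it.

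**Conclusion.** The point holds as a minor defect. The written rule gives impossible negative times to baseline, down to about -6.0 months, for same-year, year-only events when the first injection precedes 1 July. That follows from SAP 21.4 and 21.3.4 alone. The number of patients affected is unknown; 12.5% and 25% of year-only records rest on the assumed even spread over 12 or 6 months, and the share falls as events lie further back.

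The damage is to descriptive baseline times, chiefly the minimum and individual values. A reader might infer that the study's main results are at risk. The documents do not support that: the reinjection interval in SAP 15.1 is computed between injection dates, and the anti-VEGF subgroups in SAP 21.3.1 come from check boxes and treatment counts, not from dates.

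The AESI duration problem follows from the same lack of an order check, but it is unquantified. The visible text of SAP 15.2.4 does not show where duration is reported, and part of that section is redacted. It is worth closing in the same edit and supports no claim about the safety results.

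**What to change.** Add two sentences to SAP 21.4:

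1. A year-only date for an event recorded as prior history is imputed no later than the date of first injection in the study eye; for example, when the two years are equal, as the midpoint between 1 January and the injection date.
2. An imputed AESI end date is never earlier than the AESI onset date.

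The ceiling should be the injection date itself, not the day before. SAP 13.0 defines prior as strictly before only for medication and surgery, and a diagnosis could fall on the injection day.

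For same-year, year-only events the midpoint gives 0.8 months (injection 15 February 2015), 1.2 (15 March), 2.2 (15 May) and 3.0 (30 June). A plain cap gives 0.0 for every injection before 1 July and leaves later injections as they are now. Either removes the negatives; the choice between them is a matter of preference and should be written down before programming.

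The cost is two sentences and a small change to date derivation. No new data are needed, and complete dates are unaffected.

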### **21.5 OUTLIERS**

No adjustment for outliers will be done. Any outliers will be reviewed before the database lock during the data review process and decision documented in the appropriate documentation.

## **22.0            CHANGES TO ANALYSES SPECIFIED IN PROTOCOL**

The changes to the analyses specified in the original protocol, dated 24 July 2018, are specified below:

In protocol Section 14.2.2.3.2 it is specified that reason of initial injection and for reinjection will be described. Reason for initial injection is not collected in the eCRF and therefore only reason for reinjection will be described.

No analyses will be performed on the contralateral eye with the exception of AESIs (Section 15.2.4) and select measures of ophthalmic history and current ophthalmic conditions (Section 10.2).

**DOCUMENT HISTORY PAGE**

Effect Date	Revision Number	Primary Author	Description of Change
24 JUL 2019	V1.0	[REDACTED]	New
